### 12.3.2. Serious Adverse Events

Any SAE experienced by a subject after the subject signs the ICF and before End of Study or Early Termination, is to be recorded on an SAE Form, regardless of the event relationship to daclizumab. For reporting timelines and procedures, see Section 12.3.3.

Subjects will be followed for all SAEs until the end of the 4 month safety follow-up. Thereafter, the event should be reported to Biogen SABR or designee only if the Investigator considers the SAE to be related to study treatment.

Any SAE ongoing when the subject completes the study or discontinues from the study will be followed by the Investigator until the event has resolved, stabilized, or returned to baseline status.

### 12.3.3. Immediate Reporting of Serious Adverse Events

In order to adhere to all applicable laws and regulations for reporting an SAE, the study site must formally notify Biogen SABR or designee within 24 hours of the study site staff becoming aware of the SAE. It is the Investigator's responsibility to ensure that the SAE reporting information and procedures are used and followed appropriately.

#### Reporting Information for SAEs

Any Serious Event that occurs between the time that the subject has signed informed consent and End of Study or Early Termination Visit must be reported to Biogen SABR or designee within 24 hours of the study site staff becoming aware of the event.

A report ***must be submitted*** to Biogen SABR or designee regardless of the relationship to daclizumab or the severity of the event.

To report initial or follow-up information on a Serious Event, fax or email a completed SAE form to the following:

**Fax:** see Study Reference Manual

**Email:** [REDACTED] <mailto:>

### 12.3.4. Deaths

Death is an outcome of an event. The event that resulted in death should be recorded and reported on the appropriate CRF. All causes of death must be reported as SAEs. The Investigator should make every effort to obtain and send death certificates and autopsy reports to Biogen SABR or designee.

### 12.3.5. Suspected Unexpected Serious Adverse Reactions

Suspected unexpected serious adverse reactions (SUSARs) are SAEs that are unexpected and judged by the Investigator or Biogen to be related to the study treatment administered.

Biogen or designee will report SUSARs to the appropriate regulatory authorities and Investigators as required, according to local law.

CONFIDENTIAL

The information contained herein may not be used, disclosed, or published without the written consent of Biogen MA Inc.

## **12.4. Procedures for Handling Special Situations**

### **12.4.1. Reporting Pregnancy**

The Investigator should refer to the approved local label for guidance if female subjects become pregnant or are considering becoming pregnant during the study.

At each routine visit, female subjects of childbearing potential will be asked about their pregnancy status and possible pregnancies/spontaneous abortions since the last visit or contact. Spontaneous abortions are considered to be SAEs and must be reported as such.

If the partner of a male subject receiving daclizumab becomes pregnant at any time during the study, the Investigator should follow the pregnancy outcome and report any congenital anomaly or birth defect as an SAE to Biogen or designee.

### **12.4.2. Overdose**

An overdose is any dose of study treatment given to a subject or taken by a subject that exceeds the dose described in the protocol. Overdoses are not considered AEs; however, all overdoses should be recorded on an Overdose Form and faxed to Biogen SABR or designee within 24 hours. An overdose should be reported even if it does not result in an AE. Overdoses do not need to be recorded in the CRF; dosing information is recorded on a CRF.

### **12.4.3. Medical Emergency**

In a medical emergency requiring immediate attention, study site staff will apply appropriate medical intervention, according to current standards of care.

## **12.5. Investigator Responsibilities**

The Investigator's responsibilities include the following (refer to Section 12.1):

- Review all AEs to determine seriousness and fulfillment of collection criteria.
- Monitor and record all SAEs, regardless of the relationship to daclizumab.
- Determine the relationship of each SAE to daclizumab.
- Determine the onset and resolution dates of each SAE.
- Record all pregnancies.
- Complete the appropriate form for each SAE, pregnancy and overdose and fax or email it to Biogen SABR or designee within 24 hours of the study site staff becoming aware of the event.
- Pursue SAE follow-up information actively and persistently. Follow-up information must be reported to Biogen SABR or designee within 24 hours of the study site staff becoming aware of new information.
- Ensure all SAE reports are supported by documentation in the subjects' medical records.

CONFIDENTIAL

The information contained herein may not be used, disclosed, or published without the written consent of Biogen MA Inc.

- Report SAEs to local institutional review board (IRB)/ethics committees (ECs), as required by local law.

## **12.6. Biogen Responsibilities**

Biogen's responsibilities include the following:

- Before study site activation and subject enrollment, the Clinical Monitor or designee is responsible for reviewing with study site staff the definitions of AE and SAE, as well as the instructions for monitoring, recording, and reporting SAEs.
- Determine the expectedness of all SAEs.
- Biogen is to notify all appropriate regulatory authorities, central ECs, and Investigators of SAEs, as required by local law, within required time frames.

CONFIDENTIAL

The information contained herein may not be used, disclosed, or published without the written consent of  
Biogen MA Inc.

## **13. STATISTICAL CONSIDERATIONS**

### **13.1. Sample Size Justification**

This study will enroll approximately 100 subjects. The sample size is estimated based on the proportion of subjects who are relapse-free at Month 6.

Assuming a drop-out rate of 10%, the evaluable sample size will be 90. A two-sided 95% confidence interval (CI) for a single proportion of subjects on daclizumab 150 mg remaining free of relapses at the end of Month 6 will extend between 8.3% and 6.7% from the observed proportion for an expected proportion of 80% to 88%, respectively.

### **13.2. Analysis Population**

The analysis population is based on intent-to-treat (ITT), where the subjects should receive at least 1 dose of the medication during follow-up. Subjects discontinuing treatment will also be included in the analysis.

### **13.3. Methods of Analysis**

Baseline disease and demographic characteristics will be summarized overall. The demographic profile (age, sex, and race/ethnicity), relevant medical history, MS disease history, MS treatment prior to start of natalizumab treatment, and concomitant medications and therapies used will be listed and summarized using the appropriate descriptive statistics for continuous and categorical variables.

Descriptive analyses corresponding to the specific research objectives will be performed to characterize the subjects studied. Continuous variables will be reported as mean, standard deviation, median, 25th and 75th percentile (Q1, Q3), minimum and maximum where appropriate. Categorical variables will be summarized as frequencies and percentage. Proportions will be presented with exact 95% CIs as further specified in the statistical analysis plan (SAP).

Details on handling of all missing data, which are common in observational studies, will be described fully in the SAP. The proportion of missing data will be reported for each measured variable in the study. In general, missing data will not be imputed and the data will be analyzed as they are recorded in the study electronic case report forms (eCRFs).

All computations and generation of tables, listings and data for figures will be performed using SAS® version 9.3 or higher (SAS Institute, Cary, NC, USA).

Analyses corresponding to the specific research objectives of the study are described in the sections below.

### **13.4. Primary Endpoint Analysis**

#### **13.4.1. Efficacy Analysis**

The proportion of subjects relapse-free at Month 6 will be estimated using the Kaplan-Meier approach. This will be calculated as 1 minus the proportion of subjects with relapses at Month 6.

CONFIDENTIAL

The information contained herein may not be used, disclosed, or published without the written consent of  
Biogen MA Inc.

For the Kaplan-Meier approach, the time to relapse is the number of days from the date of the first dose of daclizumab to the date of first relapse, or end of study, whichever comes first. The Cox proportional hazard model will be used to estimate the hazard ratio of relapses within subject subgroups of interest. The subgroups of interest will be defined in the SAP.

The proportion of subjects relapse-free 6 months before and 6 months after switching to daclizumab will be compared using McNemar's Test for subjects who had relapse information available at the above time points.

For primary endpoints, sensitivity analyses will be performed on the ITT population excluding those patients who missed 2 or more consecutive doses within 6 months. Additional details regarding the sensitivity analysis will be described in the SAP.

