## **10.5. Treatment Schedule Modification**

Subjects who experience a significant change in their medical status (e.g., neurological worsening/suspected MS relapse, possible injection-site reaction, infection, cutaneous event, fever, abdominal pain, persistent diarrhea, jaundice, nausea, vomiting, pruritus) must contact the Study Neurologist as soon as possible and no more than 48 hours after symptom onset. The subject should then be evaluated by the Study Neurologist within no more than 72 hours for physical and neurological assessments and further treatment recommendations if appropriate. These subjects should not administer additional daclizumab until they have been evaluated by the Study Neurologist or their backup

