The information contained herein may not be used, disclosed, or published without the written consent of  
Biogen MA Inc.

The daclizumab permanent discontinuation rate at Month 12 will be summarized as the ratio of number of subjects who had permanently discontinued daclizumab prior to Month 12 over the total number of subjects who received at least 1 dose of daclizumab in the study, along with a 95% CI for the proportion.

The number of patients who missed 2 or more consecutive doses within 6 months and within 12 months will be reported. For secondary endpoints, sensitivity analyses may be considered on the ITT population, excluding those patients who missed 2 or more consecutive doses within 6 months for endpoints evaluated at/up to 6 months, and within 12 months for endpoints evaluated at/up to 12 months. Additional details regarding sensitivity analyses will be described in the SAP.

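### The only sensitivity analysis described for the primary endpoint excludes subjects on a post-baseline event that may be related to relapse; the SAP appears to drop it without replacement, so dropout and censoring go untested

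*Protocol*

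**What the plan says.** - **Main analysis, Protocol 13.4.1:** "The proportion of subjects relapse-free at Month 6 will be estimated using the Kaplan-Meier approach". Time runs from first dose to first relapse or end of study.
- **Population, Protocol 13.2:** subjects with at least one dose. "Subjects discontinuing treatment will also be included in the analysis".
- **Sensitivity analysis, Protocol 13.4.1:** the protocol commits to one on the ITT population, "excluding those patients who missed 2 or more consecutive doses within 6 months". No other is described for this endpoint, and the detail is deferred: "Additional details regarding the sensitivity analysis will be described in the SAP".
- **Secondary endpoints, Protocol 13.5.1:** the same exclusion is optional ("sensitivity analyses may be considered on the ITT population, excluding those patients who missed 2 or more consecutive doses"). The number of patients with such gaps is to be reported.
- **Follow-up, Protocol 9.2 and 7.2:** subjects without a dose for two or more consecutive months stay under data collection. Those who discontinue treatment are followed for four more months, with relapses recorded.
- **SAP 3, 4 and 5.1:** the full analysis set is everyone with at least one dose and serves every analysis. Missing data are not imputed. A subject who stops treatment early without a prior relapse is censored at the last dosing date, and time at risk ends with the treatment period. No sensitivity analysis is named.
- **SAP 2 and 4:** the study was terminated after the market withdrawal of March 2018, with about 30 subjects enrolled, and the analyses were cut back.

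**The concern.** A sensitivity analysis is useful when it varies an assumption on which the main estimate depends. Here the vulnerable assumption is that subjects who stop, or whose follow-up is cut, have the same relapse risk as those who continue. Deleting subjects with two consecutive missed doses does not vary that assumption. It selects on something that happens after baseline and may be related to the outcome, and it removes those subjects' relapses as well as follow-up that the protocol continues to collect.

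The SAP then supplies neither the promised detail nor an alternative, and its censoring rule ends observation at the last dose for relapse-free discontinuers. A subject who stops and relapses afterwards is not captured as a failure. At stake is whether the reported Month 6 proportion can be read as applying to everyone who switched, or only to those who stayed on the drug.

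**Working it through.** **1. The plan's own figure, for scale.** Protocol 13.1: "This study will enroll approximately 100 subjects", with 10% drop-out, so 100 × 0.90 = 90 evaluable. The Wald half-width is 1.96 × √(p(1−p)/90).
- p = 0.80: 8.26 points (plan: 8.3).
- p = 0.88: 6.71 points (plan: 6.7).

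Both reproduce.

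**2. What the exclusion does.** Let n = 90, R be the relapses, m the subjects excluded, and k the relapses among the excluded. Simple proportions stand in for Kaplan-Meier, and m is an assumption because the documents give no figure.

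Estimate after exclusion = 1 − (R − k)/(n − m). It exceeds 1 − R/n only if k/m > R/n.

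With R = 18 (72/90 = 80.0%) and m = 10, break-even is k = 10 × 18/90 = 2:

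| k | after exclusion |
|---|---|
| 0 | 62/80 = 77.5% |
| 1 | 63/80 = 78.8% |
| 2 | 64/80 = 80.0% |
| 5 | 67/80 = 83.8% |
| 10 | 72/80 = 90.0% |

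With m = 5 the range is 78.8% to 84.7%; with m = 15 it is 76.0% to 96.0%. With R = 11 (79/90 = 87.8%) and m = 10, it is 86.2% at k = 0, 87.5% at k = 1, 88.8% at k = 2 and 92.5% at k = 5.

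**3. The same condition in rates.** Let S be the true relapse-free proportion, h the share of non-relapsers who miss two doses, and g the share of relapsers. After exclusion the proportion is S(1−h)/[S(1−h) + (1−S)(1−g)], which is above S only when g > h. All rates here are assumed.
- S = 0.80, h = 0.05, g = 0.30: 0.76/(0.76 + 0.14) = 84.4%.
- S = 0.84, h = 0.06, g = 0: 0.7896/(0.7896 + 0.16) = 83.2%, a fall.
- Missed doses unrelated to relapse (10% missed, 20% relapse, n = 90): in 20,000 simulated trials the estimate fell in about 52% and rose in about 46%.

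**4. What the documents say about the direction.** Protocol 10.5 names suspected relapse among the events that put dosing on hold: "These subjects should not administer additional daclizumab until they have been evaluated". It allows 48 hours for contact and 72 hours for evaluation, about 5 days in all. Protocol 10.2 allows a missed dose to be taken while less than 2 weeks have passed since its scheduled date. The hold alone therefore need not cost one dose. A stop decided after evaluation could cost two, but no section prescribes it. The same section lists infection and cutaneous events, and 10.5.1 suspends or ends dosing for liver findings. The sign cannot be settled from the text.

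**5. Size of what is not tested.** As illustration, count the protocol's 10 assumed drop-outs in 100 as not relapse-free.
- 72/90 = 80.0% becomes 72/100 = 72.0% (exact 95% CI 62.1 to 80.5).
- 79/90 = 87.8% becomes 79/100 = 79.0% (69.7 to 86.5).

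The shifts of 8.0 and 8.8 points are about as large as the half-widths in step 1 or larger.

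**The case against.** The strongest reply is that the exclusion is no longer live. The SAP assigns one full analysis set to every analysis, which already keeps all dosed subjects, and it explains its reduced scope by the early termination. Most of this stands: the exclusion appears to have been dropped. But the SAP says explicitly that the discontinuation-rate analysis is not done and says nothing comparable here, and it puts nothing in its place.

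A second reply is that the protocol's main analysis already deals with early stoppers, since it keeps discontinuers and runs to end of study, which leaves the exclusion as an adherence contrast. That is fair to the protocol. It does not carry over to SAP 5.1, which ends time at risk with treatment. SAP 5.2.2 computes the relapse rate over the study period as well as the treatment period, so relapses after stopping will be partly visible, but only on a secondary endpoint.

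A reader might infer something stronger: that the exclusion can only make the result look better, because relapse leads to withheld doses, and that it is worthless as a check. The documents do not support this. The direction depends on g against h (step 3), the hold in Protocol 10.5 lasts only until evaluation, and liver suspensions could push the estimate down. As a supplementary on-treatment figure, it has some value for judging the effect of non-adherence.

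**Conclusion.** The concern holds in a limited form. The single sensitivity analysis described for the primary endpoint conditions on a post-baseline event that may be related to relapse. Its direction is not fixed, and it does not address dropout or censoring. The SAP seems to abandon it tacitly and leaves the primary estimate with no check on whether subjects who stop early do worse.

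The magnitudes are illustrative. The 77.5% to 90.0% range rests on an assumed 10 exclusions from 90 with 18 relapses, and the 8.0 to 8.8 point shift rests on applying the protocol's 10% drop-out as failures. Neither predicts the trial's result. With about 30 subjects enrolled and an abbreviated report planned, the practical stakes are modest. So is the cost of putting it right.

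**What to change.** In SAP 5.1, state that the exclusion analysis in Protocol 13.4.1 is replaced and why, keep all dosed subjects, and add:

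- **(a) All relapses to Month 6.** A Kaplan-Meier run on the full analysis set that counts every relapse up to Month 6 from continued follow-up, including relapses after missed doses or after the last dose. Where follow-up ends sooner, censor at the last relapse assessment. The four months promised in Protocol 7.2 may not reach Month 6 for a subject who stops very early. If an on-treatment estimate is also wanted, censor at the second consecutive missed dose instead of excluding the subject, so that earlier relapses still count.
- **(b) A worst-case bound.** Count subjects who stop before Month 6 for reasons other than the market withdrawal as not relapse-free, and censor those stopped by the withdrawal. Label it a bound, since it treats a liver-related stop, for example, as a failure.

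Define a missed dose so that doses lost to the end of supply are not counted as non-adherence.

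The cost is a short SAP addition and a few extra Kaplan-Meier runs, using relapse data the protocol already collects. The bound will look less favourable than the main estimate: if about 30 subjects are dosed, each such stopper with no relapse recorded moves it by roughly 1/30, or 3.3 points.

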### **13.5. Secondary Endpoints Analysis**

#### **13.5.1. Efficacy Analysis**

The proportion of subjects relapse-free at Month 12 will be estimated using Kaplan-Meier approach. This will be calculated as 1 minus the proportion of subjects with relapses at Month 12. For the Kaplan Meier approach, the time to relapse is the number of days from the date of the first dose of daclizumab to the date of first relapse, or end of study, whichever comes first. The Cox proportional hazard model will be used to estimate the hazard ratio of relapses between subject subgroups of interest.

The proportion of subjects relapse-free 12 months before and 12 months after switching to daclizumab will be compared using McNemar's Test for subjects who had relapse information available at the above time points (study completers).

The proportion of subjects experiencing relapse requiring hospitalization and/or steroid treatment at Month 12 will be estimated using the Kaplan-Meier approach. For the Kaplan-Meier approach, the time to relapse requiring hospitalization and/or steroid treatment will be the number of days from the date of the first dose of daclizumab to the date of first relapse requiring hospitalization and/or steroids treatment, or end of study, whichever comes first. A Cox proportional hazard model will be used to estimate the hazard ratio of relapses requiring hospitalization and/or steroids treatment between subject subgroups of interest.

The ARR with 95% CI at Month 12 (calculated as the total number of relapses divided by the total number of person-years in the study at the end of Month 12 for each subject) will be estimated using a negative binomial model. If the data are under-dispersed or if the negative binomial regression does not converge, a Poisson regression model with the same covariates will be used instead. Given that subjects may have more than 1 relapse in 12 months, the number of relapses will be summarized both as a continuous variable and as a categorical variable.

The number of new Gd+ enhanced and T1 hypointense lesions at Month 6 and Month 12 and the number of new or newly enlarged T2 hyperintense lesions at Month 6 and Month 12 when compared with baseline will be summarized both as continuous variables and as categorical variables. A negative binomial model adjusting for the corresponding baseline MRI lesion counts will be used to estimate the adjusted mean and lesion mean ratio between subject subgroups of interest.

CONFIDENTIAL

The information contained herein may not be used, disclosed, or published without the written consent of  
Biogen MA Inc.

The daclizumab permanent discontinuation rate at Month 12 will be summarized as the ratio of number of subjects who had permanently discontinued daclizumab prior to Month 12 over the total number of subjects who received at least 1 dose of daclizumab in the study, along with a 95% CI for the proportion.

The number of patients who missed 2 or more consecutive doses within 6 months and within 12 months will be reported. For secondary endpoints, sensitivity analyses may be considered on the ITT population, excluding those patients who missed 2 or more consecutive doses within 6 months for endpoints evaluated at/up to 6 months, and within 12 months for endpoints evaluated at/up to 12 months. Additional details regarding sensitivity analyses will be described in the SAP.

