## 4.2. Schedule of Assessments

The schedule of assessments is presented in [Table 1](#). Assessment time points include an enrollment visit, a baseline visit, and follow-up visits at Months 1, 3, 4, 6, 9 and 12. An additional safety assessment will be performed remotely 4 months after the last study treatment dose. Subjects who discontinue treatment early will still be evaluated during the safety follow-up visit (i.e., 4 months after treatment and study discontinuation). Subjects having tentative disability progression identified near the end of the core study (e.g., Month 12) will attend additional follow-up visits 12 and 24 weeks later to confirm progression.

Magnetic resonance imaging (MRI) scans will be performed at the enrollment visit (no later than 7 days prior to the first dose of daclizumab), and at Months 1, 4, 6 and 12. MRI scans will be performed under the supervision of a trained radiologist. Ad-hoc MRI scans may be performed as needed, such as in the event of a MS relapse, in order to rule out a progressive multifocal leukoencephalopathy (PML) diagnosis.

Blood chemistry and hematology assessments will be performed at baseline and at Months 1, 3, 6, 9 and 12. Hematology assessments will include a complete blood count (CBC). Liver function tests (LFT) [alanine transaminase (ALT)/ aspartate transaminase (AST)] will be done at enrollment and monthly visits. Bilirubin testing must be done together with the first AST/ALT test at the enrollment visit. Bilirubin testing must also be done if ALT/SGPT (serum glutamic pyruvate transaminase), or AST/SGOT (serum glutamic oxaloacetic transaminase)  $>3*$ upper limit of normal (ULN), since treatment must be permanently discontinued with the concomitant elevation of total bilirubin  $>2*ULN$ .

At the end of the study, liver monitoring will be done per routine clinical practice.

A safety follow-up visit at 4 months after the last dose of daclizumab provided by the study will be conducted remotely to evaluate potential delayed safety outcomes. The assessments during the additional safety follow-up period will include all safety endpoints described in [Table 1](#). Liver function tests (LFT) will be performed only if the subject is continuing daclizumab or if the subject is within 4 months since study treatment discontinuation, and monitoring is deemed appropriate by the Investigator.

CONFIDENTIAL

The information contained herein may not be used, disclosed, or published without the written consent of  

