### **7.2. Overall Study Duration and Follow-Up**

The study will consist of a 28-day (+3 days) screening period for each subject, a 12-month treatment period, and a 4-month remote safety follow-up visit after the subject's last treatment injection. The end of the study for each subject will be the last study visit or the visit at which the subject discontinues from the study (before the 12-month visit). Each follow-up visit will include a 4-day window before and after the visit for completion of all assessments. The follow-up period will include efficacy and safety following treatment initiation of daclizumab. The end of the study overall will be defined as the end of the 12-month study follow-up period for the last patient. The 4-month safety follow-up visit will be conducted remotely after the 12-month study follow-up visits have been completed.

Subjects having tentative disability progression identified near the end of the core study (e.g., Month 12) will attend additional follow-up visits 12 and 24 weeks later to confirm progression.

Subjects may discontinue treatment at any time during the study, and they will be followed for an additional 4 months to collect data on safety, LFT, MS treatment, relapses, and the use of concomitant medications.

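### The Month 12 before/after McNemar test is limited to study completers, so a subject who relapses and then leaves the study is dropped although the outcome is already known

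*Protocol*

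**What the plan says.** Protocol 13.5.1 gives two analyses of relapse-free status at Month 12.

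- The estimate: "The proportion of subjects relapse-free at Month 12 will be estimated using Kaplan-Meier approach". Time runs from first dose to first relapse or end of study, so a relapse recorded before a subject leaves is an event.
- The paired test: relapse-free status in the 12 months before and the 12 months after the switch is "compared using McNemar's Test for subjects who had relapse information available at the above time points (study completers"). The closing words treat having relapse information and completing the study as the same thing.

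The matching Month 6 test in Protocol 13.4.1 is "compared using McNemar's Test for subjects who had relapse information available at the above time points", with no mention of completers.

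Protocol 13.2 sets the general population: "The analysis population is based on intent-to-treat (ITT), where the subjects should receive at least 1 dose of the medication during follow-up". It adds: "Subjects discontinuing treatment will also be included in the analysis". Protocol 13.3 says: "In general, missing data will not be imputed and the data will be analyzed as they are recorded".

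On follow-up, Protocol 7.2 says: "Subjects may discontinue treatment at any time during the study, and they will be followed for an additional 4 months". It ends the study for a subject at the visit where that subject leaves. Protocol 9.3 does not replace withdrawals.

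SAP section 3 uses all dosed subjects for every analysis. SAP 5.1 and 5.2 describe no McNemar test.

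**The concern.** Completing the study and having a known 12-month status are different things. A subject who relapses at Month 3 and leaves at Month 5 has failed the 12-month criterion, whatever happens later. Nothing is missing and nothing needs imputing, yet the parenthesis removes this subject.

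The removal depends on the outcome being tested. A deleted relapser who was relapse-free before the switch is a lost pair of the type free before, relapsed after. These are the pairs that show worsening. Exclusion criterion 15 bars a relapse in the 6 months before screening, so most deleted relapsers are likely to be of this type.

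At stake is whether the before/after test can detect disease returning after natalizumab, the risk that motivates the trial in Protocol 5.2 and 5.2.1. The estimate and the test of one endpoint would also describe different sets of subjects.

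**Working it through.** **The plan's own figure.** The only sizing figure is the precision in Protocol 13.1; none is given for the McNemar test. Evaluable N = 100 × (1 − 0.10) = 90. The 95% half-width is 1.96 × √(p(1 − p)/90):

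- p = 0.80: 8.26%, stated as 8.3%
- p = 0.88: 6.71%, stated as 6.7%

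Both reproduce. The point below does not depend on them.

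**Effect on the proportion (illustration).** Take 100 dosed, 10 leavers, and 72/90 = 80.0% of completers relapse-free. The all-dosed proportion lies between 72/100 (every event-free leaver later relapses) and (72 + event-free leavers)/100 (none does):

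| Leavers who had relapsed | All-dosed range |
|---|---|
| 2 | 72% to 80% |
| 5 | 72% to 77% |
| 10 | 72% |

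The completer figure can therefore be up to 8 points too high.

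**Effect on the p-value (illustration).** Exact two-sided McNemar; restored leavers are assumed relapse-free before the switch. Pairs are listed as relapsed before only versus relapsed after only.

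| Completers | Completers only | 2 relapsed leavers restored | 5 restored |
|---|---|---|---|
| 80% free after, 10% relapsed before | 7 vs 16, p = 0.093 | 7 vs 18, p = 0.043 | 7 vs 21, p = 0.013 |
| 88% free after, 5% relapsed before | 4 vs 11, p = 0.12 | 4 vs 13, p = 0.049 | 4 vs 16, p = 0.012 |
| 80% free after, 5% relapsed before | 3 vs 17, p = 0.003 | already significant | already significant |
| 88% free after, 10% relapsed before | 8 vs 10, p = 0.81 | 8 vs 12, p = 0.50 | 8 vs 15, p = 0.21 |

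Two subjects can change the conclusion in some settings and not in others.

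**Effect on power.** Assumed inputs:

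- After: 1 − 0.88² = 22.6%, the upper planning value of 88% relapse-free at Month 6 carried to Month 12 at constant hazard.
- Before: 1 − exp(−0.114 × 0.5) = 5.5%, the on-natalizumab relapse rate of 0.114 quoted in Protocol 5.2, with only 6 of the 12 months at risk because of exclusion 15.
- Before and after independent; N = 100; 10% of relapse-free subjects leave; 10%, 30% or 50% of relapsers leave.

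In all dosed subjects the expected discordant pairs are:

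- relapsed after only: 100 × 0.226 × 0.945 = 21.4
- relapsed before only: 100 × 0.055 × 0.774 = 4.3

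In completers, the relapsed-before-only pairs become 4.26 × 0.9 = 3.8. The relapsed-after-only pairs become 21.4 × 0.7 = 15.0 or 21.4 × 0.5 = 10.7 at 30% or 50% departure.

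The relapse proportion among completers is 0.226(1 − d)/[0.226(1 − d) + 0.774 × 0.9], where d is the departure rate of relapsers:

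- d = 10%: 22.6%, no distortion
- d = 30%: 0.158/0.855 = 18.5%
- d = 50%: 0.113/0.810 = 14.0%

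Simulated power of the asymptotic test at two-sided 0.05 is about 96% in all dosed subjects, and 77% or 43% in completers at d = 30% or 50%.

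**The case against.** **The main estimate is sound and the test is supportive.** This stands. Kaplan-Meier keeps these relapses.

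**The final plan has no such test.** This also stands. The SAP was written after termination at about 30 enrolled. It says some endpoints will no longer be analysed, but it never states that the McNemar comparison is withdrawn.

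**A reader might infer a flat contradiction with Protocol 13.2.** The documents do not go that far. Section 13.2 keeps subjects who stop treatment; completing concerns the study. Protocol 9.2 keeps subjects who miss 2 or more consecutive monthly doses under data collection, so only those who leave the study are lost. Protocol 4.2 does blur the distinction with its phrase "4 months after treatment and study discontinuation".

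**A reader might infer that relapse-related departure is likely.** Follow-up after stopping treatment is set at 4 months, so a subject who stops before about Month 8 need not reach Month 12. But relapse is not a listed withdrawal reason in 9.3, and a suspected relapse leads to evaluation under 10.5. The departure rates are assumed. With 22.6% relapsing, 50% departure means 11.3% of all subjects, more than the whole 10% drop-out planned in 13.1 (a Month 6 figure); 30% means 6.8%, which fits.

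**A reader might infer a false benefit for daclizumab when nothing changed.** With an equal 15% risk in both periods, completer-only rejection is about 9%, 23% and 50% at 30%, 50% and 70% departure, nearly all in daclizumab's favour. That null ignores exclusion 15, which makes about half of the before year relapse-free by selection. With an unchanged hazard and 6 months at risk before (5.5% before, 10.8% after), rejection in daclizumab's favour is below 1%, about 1% and about 6%. What remains is mainly lost ability to see worsening.

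**Conclusion.** The point holds as a flaw in the protocol's supportive Month 12 test. The completer restriction discards known outcomes and biases the test towards no worsening if relapsers leave the study more often than others. If they leave at the same rate, there is essentially no bias.

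The size cannot be fixed from the documents, which give no departure rate by relapse status, no pre-switch relapse rate for this population and no Month 12 relapse-free rate. Under the stated assumptions, power falls from about 96% to 77% or 43%. These figures illustrate the mechanism and do not predict the trial's result.

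The Kaplan-Meier estimate does not share this flaw, and the abbreviated analysis as the SAP describes it is not affected.

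**What to change.** 1. In Protocol 13.5.1, delete the words study completers and their parentheses.
2. Count every dosed subject with a relapse before Month 12 as not relapse-free, whether or not the subject stayed.
3. Run the paired comparison in all dosed subjects twice, with event-free leavers counted first all as relapse-free and then all as relapsed. In the first p-value example, with 2 of 10 leavers relapsed, this gives 7 vs 18 (p = 0.043) and 7 vs 26 (p = 0.0013). Alternatively, compare the 12-month Kaplan-Meier proportion with the pre-switch proportion using a paired bootstrap CI.
4. Do not keep known relapsers while simply omitting event-free leavers. That overstates relapse: with a true 85% relapse-free and 10% of event-free subjects leaving, it gives 0.85 × 0.9/(0.85 × 0.9 + 0.15) = 83.6%.
5. State in the SAP whether the before/after test is retained or dropped.

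Cost: a small change of wording, two extra programmed runs and no new data. The result is a range and not a single p-value. The change does not cure the separate selection of the before period by exclusion 15, which affects this comparison however leavers are handled.
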